2.1 Data analysis general information

Data will be analyzed by Novartis Oncology Biostatistics and Statistical Programming personnel according to the data analysis section 10 of the LDK378X2103 protocol, which will be available in Appendix 16.1.1 of the Clinical Study Report (CSR). Important information is

given in the following sections and details are provided, from which Appendix 16.1.9 of the CSR will be written.

The data will be analyzed using SAS version 9.4 or later, and for Bayesian modeling, R version 2.13.2 or later, and WinBUGS version 1.4.3 or later. The Bayesian modeling of the dose-toxicity relationship used for dose escalation decision making and inference for the MTD is performed using internal Novartis R library functions (OncoBayes) created by Novartis's Methodology group and are run using R version 2.13.2 or later in the MODESIM/GPSII environment.

Data from patients who signed study informed consent in centers that participate in this study will be used in the analysis; due to expected small size of enrollment at individual centers, no center effect will be assessed. Each analysis will use all data in the database up to the analysis cutoff date, determined prior to database lock. Data collected after patients' withdrawal of informed consent for further participation in the study will not be reported (except for death date which might be obtained from public records).

Final CSR

The study data will be analyzed and reported based on all patients' data of both dose escalation and expansion parts at the end of study, and a final CSR will be written. Patients treated with the MTD, or RDE if different, on the regimen (fasted or fed) during the dose escalation part, will be pooled with those receiving both the same dose and the same regimen during the expansion part. For patients undergoing intra-patient dose escalation to doses other than their initially received dose level, their post-escalation data will be listed separately. However, only data before the first intra-patient escalation will be used in summary statistics. A treatment group is defined by dose level and regimen (fasted or fed).

End of study is defined as earliest occurrence of one of the following:

1. All patients have discontinued study treatment, and all required Study evaluation completion (SEC) follow-up visit have been completed, or
2. All patients have died, have been lost to follow-up or have withdrawn consent to further participation in the study, or the last patient on treatment has been enrolled into a separate rollover study or other option for continued treatment with LDK378, whichever comes first.

The final analysis of study data will be conducted at the end of the study and all available safety and efficacy data from all patients will be analyzed. A final clinical study report (CSR) will be produced reporting all available data collected.

General presentation of descriptive summaries

Qualitative data (e.g. gender, race) will be summarized by frequency counts and percentages. Percentages will be calculated using the number of patients in the relevant population or subgroup, as the denominator.

Continuous data (e.g. age, body weight) will be summarized by appropriate descriptive statistics (i.e. mean, standard deviation, median, minimum, and maximum).

Summary statistics for PK concentrations and PK parameters will include the following, unless otherwise specified: n, mean, SD, CV% mean, geometric mean, CV% of geometric mean, median, minimum and maximum.

Data from patients enrolled during the expansion phase in the applicable disease group at the MTD/RDE will be pooled with data from patients enrolled in the dose-escalation phase, unless otherwise specified (e.g. primary analysis of dose-DLT relationship).

Unless otherwise specified, analysis of efficacy data will be presented:

- by treatment group : A treatment group is defined by both dose level and regimen (fasted or fed). Data from patients in the expansion and escalation parts in the same treatment group will be combined.
- by expansion group: for patients in the pooled LDK378 MTD/RDE group
 - patients with ALK-activated neuroblastoma,
 - patients with ALK-activated IMT.
 - patients with ALK-activated ALCL.
 - patients with all other ALK-activated tumors.

The efficacy data of patients with lymphoma evaluated by IWG (Cheson) response criteria will be summarized/listed separately from the efficacy data evaluated by RECIST 1.1.

Unless otherwise specified, all summaries of PK data will be presented by treatment group and by expansion group as defined above.

All listings will be displayed by indication, treatment group, and patient, unless otherwise specified.

For safety, PK and all other summaries, data will be presented by treatment group unless otherwise specified.

The safety summary tables will include only assessments collected during the on-treatment period unless otherwise specified. For select items, shift tables or change from baseline summaries generated for laboratory, ECG, and vital signs may use data from pre-treatment period for baseline calculations. See [Section 2.1.1](#) for key definitions of terms used in this SAP.

All data, regardless of observation period, will be listed and assessments collected in the pre-treatment or post-treatment period will be flagged in all the listings.

Subgroup analyses

If the number of patients allows (larger than or equal to 10), in addition to the population subgroups described above, efficacy endpoints (ORR) and adverse events (AEs) will also be summarized for patients in the LDK378 MTD/RDE group by the following subgroups:

- age (1 year to <7 years, 7 years to <12 years, 12 years to <18 years)

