#### 10.7.1.2 Adverse events (AEs)

All AEs recorded during the study will be summarized. The incidence of treatment-emergent AEs (new or worsening from baseline) will be summarized by primary system organ class, severity based on CTCAE version 4.03, type of adverse event, and relationship to LDK378, by treatment group. Deaths reportable as SAEs and non-fatal SAEs will be listed by patient and tabulated by primary system organ class, type of adverse event, and treatment group.

Any other information collected (e.g. start/end dates and duration of adverse event, severity or relatedness to study medication) will be listed as appropriate.

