If the observed ORR is equal to or greater than 30%, then this will be considered as preliminary evidence of substantial antitumor activity of LDK378 in ALK activated neuroblastoma. If the observed ORR is between 20% and 30% then this will be considered as evidence of moderate antitumor activity, and as limited antitumor activity if it is between 10% and 20%. If the observed ORR is less than 10% (i.e. ≤ 2 CR or PR out of 25), then insufficient antitumor activity will be declared.

Note that for a sample size of $n = 25$ (see section 10.8), if the observed ORR is greater than or equal to 20% (i.e. ≥ 5 CR or PR), then the true ORR has a posterior risk of less than 10% of being in the insufficient antitumor activity category.

A minimally informative unimodal Beta prior distribution of the true ORR is derived as follows. A priori it is assumed that the true mean of the ORR equals 20%. A true ORR of 20% is the midpoint between limited and moderate antitumor activity and serves as a compromise between a skeptical view assuming the treatment has only limited antitumor activity and an optimistic view assuming the treatment has moderate antitumor activity. The parameters of the minimally informative Beta prior distribution of the ORR are then derived as $a=1/4$ and $b=1$.

Best Overall Response

Best overall response (BOR) is the best response recorded from the start of the treatment until disease progression. Patients with a BOR of 'UNKNOWN' will be treated as non-responders when estimating ORR. If any non-palliative cancer therapy is taken while on study any subsequent assessments will be excluded from the BOR determination. MIBG response score per curie criteria will be recorded and listed for patients with neuroblastoma who had MIBG scan.

Determination of BOR per RECIST 1.1

ORR is defined as the proportion of patients with a best overall complete response (CR) or partial response (PR) per RECIST 1.1.

For patients with the primary diagnosis other than lymphoma, BOR will be based on the overall lesion assessment per RECIST 1.1. The evaluation of overall lesion response at each assessment is a composite of the target lesion response, non-target lesion response and presence of new lesions (for details see Protocol Appendix 5).

The BOR for each patient is determined from the sequence of overall (lesion) responses according to the following rules:

- CR = at least two determinations of CR at least 4 weeks apart before progression

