2.8 Safety analyses

The safety set will be used for all safety analyses with the exception of the DLT analyses that will use the DDS.

The overall observation period will be divided into three mutually exclusive segments:

- Pre-treatment period: from day of patient's informed consent to the day before first dose of study drug
- On-treatment period:
 - For discontinued patients, from day of first dose of study drug to 30 days after last dose of study drug
 - For ongoing patients, from day of first dose of study drug to the data cut-off date
- Post-treatment period: starting at day 31 days after last dose of study drug

The safety summary tables will include only assessments collected no later than 30 days after study drug discontinuation and assessments prior to the data cut-off date for on-going patients, unless otherwise specified.

For select items, shift tables or change from baseline summaries generated for laboratory, ECG, vital signs and change score (including Karnofsky/Lansky) generation may use data from pre-treatment period for baseline calculations.

All data, regardless of observation period, will be listed and visits/cycles collected in the pre-treatment or post-treatment period will be displayed in all the listings.

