2.8.1 Adverse events (AEs)

AEs will be coded using the latest version of MedDRA available prior to clinical database lock and will be graded using Common Terminology Criteria for Adverse Events (CTCAE) version 4.03. If CTCAE grading criteria exists for an AE, grades 1, 2, 3, or 4 corresponding to the severity of mild, moderate, severe, and life threatening, respectively, will be used. CTCAE grade 5 (death) will not be used in this study; rather, this information will be collected on the "End of Treatment" or "Study evaluation completion" eCRF pages.

All AE summaries will be summarized (frequency counts and percentages) by system organ class and/or preferred term, and maximum severity grades, except where otherwise noted. A patient with multiple CTC grades for an AE will be summarized under the maximum CTC grade recorded for the event.

The following AE summaries will be produced:

- AEs regardless of study drug relationship
- AEs suspected to be study drug related
- All deaths, by primary SOC and PT
- On-treatment deaths, by primary system organ class and preferred term
- SAEs regardless of study drug relationship
- SAEs suspected to be study drug related
- AEs associated with study drug discontinuation
- AEs requiring dose adjustment or interruption
- AEs requiring significant additional therapy
- AEs excluding SAEs
- In addition, AEs regardless of study drug relationship will be summarized by PT and age group for MTD/RDE patients.

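### The rule that cuts summaries at the first intra-patient dose escalation conflicts with the plan's own definitions of its safety tables, BOR, DOR and PFS

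*SAP*

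**What the plan says.** SAP 2.1 (Final CSR) and protocol section 10 carry the same rule for patients who undergo intra-patient dose escalation: "their post-escalation data will be listed separately", and "only data before the first intra-patient escalation will be used in summary statistics". Neither exempts any endpoint, and SAP Table 4-1 records no exception.

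Other parts of the plan set windows that do not stop at escalation:

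- SAP 2.1, on the final analysis: "all available safety and efficacy data from all patients will be analyzed".
- Protocol 10.7.1.2: "All AEs recorded during the study will be summarized".
- SAP 2.8, on-treatment period for patients who have discontinued: "from day of first dose of study drug to 30 days after last dose of study drug".
- SAP 2.8.1 plans a table titled "All deaths, by primary SOC and PT", plus SAE tables.
- SAP 2.6: "Best overall response (BOR) is the best response recorded from the start of the treatment until disease progression". DOR in the same section runs to progression or death.
- SAP 2.7: PFS runs to first progression or death. SAP 2.7 and 5.4.1 each list six censoring reasons, and dose escalation is not among them.
- SAP 2.4.1 defines cumulative dose over the whole study.

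**The concern.** A patient who escalates and later progresses has a PFS event that SAP 2.1 excludes and SAP 2.7 requires. If the cut governs, the plan gives no censoring date or reason for that patient. If the endpoint sections govern, the sentence in 2.1 is wrong for efficacy. The same clash affects a death or SAE on the higher dose and a response first confirmed there. Two programmers following the SAP could produce different tables.

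The affected patients are not a random subset. Protocol 6.2.3.2 allows escalation only after four cycles free of drug-related toxicity of grade 2 or above, so a literal cut removes later follow-up from patients selected for tolerating the drug. The new dose may be any evaluated level up to the MTD, so some dropped events could occur at the dose carried forward. The same protocol section uses first-cycle data at the new dose in the clinical safety assessment for dose decisions, which makes leaving them out of the final tables hard to defend.

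**Working it through.** **1. The texts side by side, for a patient who has escalated**

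| Output | Window in its own section | Result under the SAP 2.1 cut |
|---|---|---|
| Deaths, SAEs, AEs (SAP 2.8, 2.8.1) | First dose to 30 days after last dose; the all-deaths table has no stated window | Events after escalation listed only |
| BOR (SAP 2.6) | Treatment start to progression | Later responses not counted |
| DOR (SAP 2.6) | First response to progression or death | End date undefined |
| PFS (SAP 2.7, 5.4.1) | Treatment start to progression or death | Event excluded, no censoring rule |
| Cumulative dose (SAP 2.4.1) | Whole study | Truncated |

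No endpoint section mentions escalated patients, and SAP 2.1 does not say how its cut applies endpoint by endpoint.

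**2. When the cut can first bite.** Inputs are a 21-day cycle (protocol 4.1), no escalation within the first four cycles (protocol 6.2.3.2), and tumor assessment on Day 15 of Cycles 2, 4 and 6 and less often afterwards (protocol 7.2.1).

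- Earliest escalation: 4 × 21 + 1 = day 85, or 85 / 30.4375 = 2.8 months (month length from SAP 5.3).
- DLT window: days 1 to 21, all before day 85.
- Last PK sample in protocol Table 7-5, C4D1: 3 × 21 + 1 = day 64, before day 85. (The trough list in SAP 2.10 runs to C6D1, day 106, but the protocol schedule does not.)
- C2D15: 21 + 15 = day 36. C4D15: 63 + 15 = day 78. C6D15: 105 + 15 = day 120.

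SAP 2.6 needs two RECIST determinations at least 4 weeks apart. Days 36 and 78 are 42 days apart, so a response first seen on day 36 can be confirmed before any escalation. For a patient escalated on day 85, a response first seen on day 78 would be confirmed on day 120, after the cut, and anything first seen on day 120 or later is also lost.

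The planned PFS time points are 2, 4, 6, 8, 10 and 14 months. For that patient only the 2-month point (2 × 30.4375 = day 61) is covered; the 4-month point is day 122.

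**3. How many patients could be affected.** The documents do not say how many escalated. Amendment 6 gives 40 escalation-part patients (25 fasted, 15 fed), and Amendment 8 gives 83 treated in total. Protocol 6.2.3 requires at least 6 patients at each MTD/RDE. Assuming exactly 6 there:

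- Fasted: 25 − 6 = 19. Fed: 15 − 6 = 9. Sum: 28.
- 28 / 83 = 34%.

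The range is therefore 0 to about 28. Any patient who started fasted at 560 mg/m², above the 510 mg/m² MTD/RDE, lowers the ceiling, as does anyone who left or had drug-related toxicity of grade 2 or above within four cycles.

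**4. The design figures are not touched.** For the neuroblastoma rule of at least 5 responses in 25, the exact binomial gives 0.0980 at a true ORR of 10% and 0.9095 at 30%, matching the stated 9.8% and 91.0%. Those patients are at the MTD/RDE and, if the RDE equals the MTD, cannot escalate.

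**The case against.** The best case for the plan is that the cut is deliberate. It is identical in protocol and SAP, so it is prespecified. Most displays are by treatment group, meaning dose level and regimen, and there it prevents events or responses at a higher dose from being credited to a lower one. The SAP specifies no all-dose safety total; only protocol 10.7.3 mentions an overall Kaplan-Meier analysis. Post-escalation data are still listed. The more specific endpoint sections could be read as overriding a general sentence.

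Much of this stands. The cut is right for by-dose-level tables, it is not an SAP departure, and nothing goes unreported. Two parts do not stand. Listings do not replace incidence tables for deaths and SAEs. And the sentence in 2.1 is the only text written for escalated patients, so it is not clear that the endpoint sections override it.

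A reader might also infer that every later death and progression vanishes from the tables. The documents do not settle that, because other SAP text points the other way. Nor do they support saying that the longest-treated patients are the ones lost: four cycles is a minimum, only patients who actually escalate are affected, and long-treated patients at the MTD are untouched. Setting day 85 against the study's five years and three months would suggest that only a few percent of follow-up is summarized, but no patient's exposure or escalation date is given.

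**Conclusion.** The plan gives incompatible instructions for post-escalation data on deaths, SAEs, BOR, DOR and PFS. Followed literally, the cut omits those events from the tables for escalated patients. This should be resolved before database lock.

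The scope is bounded. The Cycle 1 DLT endpoint, PK sampling under the protocol schedule and the nominal Cycle 2 and Cycle 4 tumor assessments precede any escalation. The MTD/RDE expansion-group analyses are essentially unaffected, provided the RDE equals the MTD on each regimen; SAP 2.5 gives a single MTD/RDE value for each. The number affected is unknown, from 0 to about 28 of 83, and the upper end rests on the assumption of six patients at each MTD/RDE. No primary-endpoint result, sample-size figure or neuroblastoma decision rule changes.

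**What to change.** - Restrict the pre-escalation cut in SAP 2.1 to by-dose-level displays: AE rates, laboratory, ECG and PK by treatment group.
- Summarize deaths, SAEs, AEs leading to discontinuation and AESIs for all patients over the whole on-treatment period. Show post-escalation events separately so that they are not attributed to the lower dose.
- State that BOR, PFS and DOR follow SAP 2.6 and 2.7 from treatment start under the initial treatment group. Give the pre-escalation version as a sensitivity analysis, with its censoring date defined, and flag responses first seen after escalation.
- Report the number of escalated patients and record the change in SAP Table 4-1.

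The cost is SAP wording and one extra table set from data already collected. The downside is that a response first reached at a higher dose counts under the initial group, which is why the flag and the sensitivity analysis are needed.

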2.1.1 General definitions

Study drug and study treatment

Study drug and study treatment both refer to the Novartis investigational drug, LDK378 (ceritinib) and will be used interchangeably. LDK378 will be provided to investigation sites and administered once daily by mouth, or by NG tube or G-tube.

Date of first/last administration of study drug

The date of first administration of study drug is defined as the first date when a non-zero dose of study drug was administered and recorded on the Dosage Administration Record (DAR) eCRF. For the sake of simplicity, the date of first administration of study drug will also be referred as start date of study drug.

The date of last administration of study drug is defined as the last date when a non-zero dose of study drug was administered and recorded on DAR eCRF. This date will also be referred as last date of study drug.

Study day

The study day for all assessments (e.g. tumor assessment, death, disease progression, tumor response, performance status, adverse event onset, laboratory abnormality occurrence, vital sign measurement, dose interruption etc.) will be calculated using the start date of study drug as the origin. For assessments occurring after or on the start date of study drug, study day will be calculated as:

$$\text{Study Day} = \text{Date of assessment/Event date} - \text{start date of study drug} + 1.$$

The first day of study drug is therefore study day 1.

For any assessment or events such as baseline disease characteristics or medical history (e.g., time since diagnosis of disease) occurring prior to the start of the study drug, study day will be negative and will be calculated as:

$$\text{Study Day} = \text{Date of assessment/Event date} - \text{start date of study drug}.$$

The study day will be displayed in the data listings. If an event starts before the reference start date, the study day displayed on the listing will be negative.

Baseline

Baseline is the result of an investigation describing the “true” uninfluenced state of the patient. The last available assessment before or on the start date of study drug is defined as “baseline” value or “baseline” assessment, unless otherwise stated. If the assessment is planned to be performed prior to the first dose of study drug in the protocol and the assessment is performed on the same day as the first administration of study drug, it will be assumed that it was performed prior to study drug administration, if assessment time or first dose time is not collected or is missing. If assessment and first dose times are collected, the observed time point will be used to determine pre-dose on study day 1 for baseline calculation. Unscheduled assessments will be used in the determination of baseline. See [Section 5.5.2](#) for further details on derivation of baseline for laboratory data and ECGs.

Patients who start treatment and discontinue from the study on the same day may have two different sets of data collected on study day 1, one being reported to the cycle 1 day 1 visit, the other reported to the end of treatment (EOT) visit. Data reported at the EOT visit are not eligible for baseline selection.

Cohort

A group of newly enrolled patients treated at a specific dose and regimen (i.e. treatment group) at the same time. There may be more than one cohort at the same dose level.

Treatment group

Treatment group will generally be determined by the initially planned LDK378 dose level in mg/m² and regimen on Cycle 1 Day 1. For safety analysis, treatment group will be determined by dose and regimen received. Further details on the determination of treatment received is given in [Section 2.2](#). A treatment group can include several cohorts of patients who have received the same dose level and regimen but were recruited at the different point during the study. A treatment group may consist of one or more cohorts.

2.2 Analysis sets

A patient is considered to be enrolled into the study if they have signed study informed consent. Only patients who have signed study informed consent prior to study procedures will be included in the analysis data sets.

Full analysis set

The Full Analysis Set (FAS) includes all patients who received at least one dose of LDK378. Patients will be classified according to the intended/planned treatment. The FAS will be used for all listings of raw data. Unless otherwise specified, the FAS will be the default analysis set used for all analyses.

The planned treatment will be based on the first dosing record. The corresponding fasted/fed status will be determined as per [Table 2-1](#) below as per protocol.

Table 2-1 Dose level and fasted/fed status

Dose Levels	Fasted/Fed Status
200 mg/m ²	Fasted
300 mg/m ²	Fasted
450 mg/m ²	Fasted
510 mg/m ²	Fasted
560 mg/m ²	Fasted
320 mg/m ²	Fed
400 mg/m ²	Fed
500 mg/m ²	Fed

Safety set

The safety set includes all patients who received at least one dose of LDK378.

The patients will be classified according to treatment received, where treatment received is defined as:

1. The actual dose level (mg/m^2) is the planned dose level if any actual total daily dose administered is equal to the value of “the planned dose levels ([Table 2-1](#)) * BSA (m^2) rounds to the nearest 50 mg”. For 25/75 mg, either rounding up or rounding down is acceptable.
2. The first actual dose level in the study (converts actual total daily dose administered / BSA (m^2) and maps to nearest planned dose levels) if the planned dose level was never received.

BSA = The last available BSA measurement on or before dosing date will be used in the calculation for actual dose level.

For example, if a patient from 500 mg/m^2 fed group doesn't meet the first criteria, and the first actual dose level in the study is 150 mg. Suppose this patient has BSA=0.45 m^2 on/before the first dose, then the first actual dose level in the study=actual total daily dose administered / BSA (m^2)=333 mg/m^2 , which will be rounded to the nearest planned dose level 320 mg/m^2 fed.

Dose determining set

The dose determining analysis set (DDS) consists of all patients from the safety set who *either* meet the minimum exposure criterion and have sufficient safety evaluations *or* discontinue earlier due to DLT in the escalation phase.

A patient is considered to have met the minimum exposure criterion if s/he received at least 16 out of the 21 planned once daily doses of LDK378 in the first 21 days of dosing. Patients who do not experience DLT during the first cycle are considered to have sufficient safety evaluations if they have been observed for at least 21 days following the first dose, and are considered by both the Sponsor and Investigators to have sufficient safety data to conclude that a DLT did not occur.

Patients who do not meet these minimum safety evaluation requirements and who did not discontinue earlier due to a DLT will be regarded as ineligible for the DDS.

Pharmacokinetic analysis set

The pharmacokinetic analysis set (PAS) consists of all patients who received at least one dose of LDK378 and have at least one evaluable pharmacokinetic (PK) sample.

Depending on whether the sample is part of a full profile or a trough collection, the specific criteria are listed as follows.

An evaluable full PK profile is defined as:

1. On the PK collection day, no vomiting occurred within 4 hours of dosing on the full PK sampling day (i.e., no vomiting within 4 hours after Cycle 1 Day 1 dose or after Cycle 2 Day 1 dose), AND
2. On the PK collection day, the patient takes study drug according to the originally assigned dose, AND
3. The patient takes study drug according to the originally assigned dose for at least 5 consecutive days without interruption or dose modification prior to the PK sampling day (except for Cycle 1 Day 1, i.e., only applicable to Cycle 2 Day 1), AND

4. On the PK collection day, the patient takes study drug under the originally assigned prandial condition, AND
5. The patient takes study drug under the originally assigned prandial conditions, i.e., dose administered without food for patients in the fasted cohort, or dose administered with light snack food for patients in the fed cohort, for at least 5 consecutive days prior to the PK sampling day (except for Cycle 1 Day 1, i.e., only applicable to Cycle 2 Day 1), AND Additionally, an entire profile can be considered non-evaluable as per scientific judgment of the clinical pharmacology expert even if the above criteria are fulfilled. Reason will be documented.

An evaluable trough PK concentration (C_{min}) is defined as:

1. the patient takes study drug according to the originally assigned dose for at least 5 consecutive days prior to the PK sampling day (except for Cycle 1 Day 1 in dose escalation and expansion phases), AND no vomiting occurs within 4 hours following the last dose intake prior to the PK sample draw,
2. For the pre-dose or 24 hour post-dose sample, draw must occur between 0 to 6 hours before the dose that is immediately after, AND
3. The patient takes study drug under the originally assigned prandial conditions, i.e., dose administered without food for patients in the fasted cohort, or dose administered with light snack food for patients in the fed cohort, for at least 5 consecutive days prior to the PK sampling day (except for Cycle 1 Day 1), AND Additionally, a sample can be considered non-evaluable as per scientific judgment of the clinical pharmacology expert even if the above criteria are fulfilled. Reason will be documented.

A patient belongs to PAS if he/she has either an evaluable full PK profile or an evaluable trough PK sample.

Any blood samples missing blood collection date or time, or missing associated study drug dosing date or time will be excluded.

Frequency counts and percentages (using FAS as denominator) of patients in each of the above defined analysis sets will be summarized. In addition, listings of patients included in each of the analysis sets will be provided.

Section 2.3.5 provides further details regarding the derivation of the analysis sets.

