### **10.1.2 Safety set**

The safety set includes all patients who received at least one dose of LDK378.

On the specified regimen, patients will be classified according to dose level received, where dose level received is defined as:

1. The dose level assigned if it was received at least once, or
2. The first dose level received in the study, if the assigned dose level was never received.

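### The SAP's safety-set fallback omits the protocol's within-regimen limit, so applied literally it can tabulate a fed patient as fasted, or the reverse

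*SAP*

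**What the plan says.** **Protocol 10.1.2 (Safety set)** opens with the regimen held fixed: "On the specified regimen, patients will be classified according to dose level received". The dose level is then the assigned one if it was received at least once, and otherwise the first level received.

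**SAP 2.2 (Safety set)** turns this into two programming rules.

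- Rule 1: the actual dose level "is the planned dose level if any actual total daily dose administered is equal to the value of" planned level × BSA, rounded to the nearest 50 mg. Here the SAP identifies the planned dose levels with Table 2-1.
- Rule 2, the fallback: divide the first actual daily dose by BSA; the result "maps to nearest planned dose levels) if the planned dose level was never received". No regimen limit is stated.

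**SAP 2.2, "Table 2-1 Dose level and fasted/fed status"**, is a single list of eight levels, each with one regimen: 200, 300, 450, 510 and 560 mg/m² fasted; 320, 400 and 500 mg/m² fed. For planned treatment in the FAS, regimen is read off this table: "The corresponding fasted/fed status will be determined as per" it.

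**SAP 2.1.1 (Treatment group)** says "For safety analysis, treatment group will be determined by dose and regimen received" and sends the reader to Section 2.2 for how treatment received is determined.

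**SAP Table 4-1**, the list of changes from protocol-specified analyses, contains only best-overall-response items.

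**The concern.** Rule 2 uses the same term that rule 1 has just tied to Table 2-1. A programmer who takes it at face value will search all eight levels. Because each level carries one regimen, choosing the nearest level also chooses fasted or fed. A patient could then appear in the safety tables under a regimen he or she did not take, which the protocol wording rules out.

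Safety results are presented by regimen and dose level (protocol 10.7.1.1). Exposure and dose-intensity summaries also use the Safety set (SAP 2.4.1). Describing the fasted and fed states separately is part of the study's objectives, and protocol 6.2.2 estimates that a low-fat meal raises steady-state exposure 1.58-fold. Escalation cohorts have 3 to 6 patients, so one misfiled patient would visibly change the percentages in a small group.

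**Working it through.** **Inputs.** Levels and regimens from SAP Table 2-1; rules 1 and 2 and the worked example from SAP 2.2; 50 mg rounding from protocol 6.1.1 and SAP 2.2.

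**Step 1: reproduce the SAP's example.** A patient in the 500 mg/m² fed group first receives 150 mg. The SAP continues: "Suppose this patient has BSA=0.45" m².

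- Planned dose: 500 × 0.45 = 225 mg. The SAP accepts rounding either way, so 200 or 250 mg would satisfy rule 1. A dose of 150 mg does not, and the example supposes that no other dose did.
- Actual level: 150 / 0.45 = 333.3 mg/m².
- Distance to 320 fed is 13.3; distance to 300 fasted is 33.3.

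The result, 320 mg/m² fed, agrees with the SAP ("which will be rounded to the nearest planned dose level 320"). It is the same whether the search covers all eight levels or the fed levels only, so the example does not show which search is meant.

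**Step 2: whole-table search.** Ordered levels are 200 fasted, 300 fasted, 320 fed, 400 fed, 450 fasted, 500 fed, 510 fasted and 560 fasted. The boundary between neighbours is (lower + upper) / 2:

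| Neighbouring levels | Boundary (mg/m²) | Regimen changes? |
|---|---|---|
| 200 / 300 | 250 | no |
| 300 / 320 | 310 | yes |
| 320 / 400 | 360 | no |
| 400 / 450 | 425 | yes |
| 450 / 500 | 475 | yes |
| 500 / 510 | 505 | yes |
| 510 / 560 | 535 | no |

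The nearest level is therefore fasted below 310, from 425 to 475, and above 505; it is fed from 310 to 425 and from 475 to 505. A fed patient in the fallback crosses in the first set of intervals and a fasted patient in the second.

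**Step 3: the two readings compared.** Each case assumes that rule 1 is never met.

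| Planned group | BSA (m²) | First dose (mg) | mg/m² | Whole table | Own regimen only |
|---|---|---|---|---|---|
| 500 fed | 0.45 | 150 | 333 | 320 fed | 320 fed |
| 500 fed | 0.45 | 100 | 222 | 200 fasted | 320 fed |
| 500 fed | 1.0 | 300 | 300 | 300 fasted | 320 fed |
| 500 fed | 1.0 | 450 | 450 | 450 fasted | tie: 400 or 500 fed |
| 510 fasted | 1.0 | 400 | 400 | 400 fed | 450 fasted |
| 510 fasted | 1.5 | 500 | 333 | 320 fed | 300 fasted |

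Within regimen, no crossing can occur. The search does produce exact ties. For fed levels the boundaries are (320 + 400)/2 = 360 and (400 + 500)/2 = 450. For fasted levels they are 250, (300 + 450)/2 = 375, (450 + 510)/2 = 480 and 535.

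**Step 4: how far rule 1 protects.** A fed patient at 320 mg/m² with BSA 0.82 m² has a planned dose of 320 × 0.82 = 262.4 mg, which rounds to 250 mg. That is 250 / 0.82 = 304.9 mg/m², below the 310 boundary, but rule 1 is met and the patient stays in 320 fed. The Step 2 intervals therefore matter only after rule 1 has failed on every dosing day.

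**The case against.** The strongest reply is that the SAP nowhere says the search crosses regimens. Rule 2 is silent. Its only example begins and ends with a fed patient. SAP 2.1.1 defines the safety group by dose and regimen received, protocol 10.1.2 holds regimen fixed, and Table 4-1 declares no change. The fasted/fed lookup is stated for planned treatment in the FAS, not for rule 2. Read together, these suggest a within-regimen search was intended.

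Much of this stands. A reader might infer that the SAP prescribes cross-regimen mapping; the text does not go that far. But intent does not close the gap. SAP 2.1.1 defers to Section 2.2, which is the rule in question, and the example fits both readings.

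A reader might also infer that the fallback, once used, is usually wrong, because five of the eight levels are fasted and much of the dose range lies nearest one of them. The documents do not support that. Landing on a fasted level is an error only for a fed patient. No distribution of fallback doses is given, and doses in 50 mg steps do not reach every mg/m² value at every BSA.

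The limits on impact also stand. The FAS is classified by planned treatment and is used for efficacy (SAP 2.6), the MTD/RDE is already recorded as determined (SAP 2.5), and all doses are listed with reasons for change (SAP 2.4.1), so an odd classification could be noticed. The 1.58-fold figure comes from healthy adults and does not measure bias in these tables.

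**Conclusion.** The point holds as an omission in the SAP's programming rule. Rule 2 lacks the protocol's regimen limit, and its literal application to Table 2-1 can give a safety grouping that the protocol does not allow, in either direction and over the intervals in Step 2. The departure is not declared.

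Its size is small. It reaches only patients who never once received planned level × BSA rounded to 50 mg; the documents do not give their number, and it may be zero. It concerns Safety-set tabulations by treatment group, not FAS efficacy analyses and not dosing. The intervals assume a whole-table search; if the programs already search within regimen, nothing is misfiled and only the wording needs correcting.

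**What to change.** In SAP 2.2, safety-set rule 2, write: *maps to the nearest planned dose level within the patient's own regimen (Table 2-1)*. Add a tie rule for tabulation, since 450 mg/m² in a fed patient is equally far (50 mg/m²) from 400 and 500. Any rule fixed before the tables are run will do.

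This restores the protocol 10.1.2 restriction, leaves the SAP's worked example unchanged and makes a change of regimen impossible. It costs one or two sentences and a check that the classification program filters Table 2-1 by regimen before searching. A count of patients classified by rule 2 in the study report would show whether the point had any effect.
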